Removal of use of insulin as a prohibited medication.	To enable recruitment of representative target population of obese men with type 2 diabetes requiring insulin.
Removal of Cyp3A4 and Cyp2A6 modifying concomitant medications.	BGS649 has been shown not to be a substrate or inducer of major Cytochrome (CYP) 450 enzymes and is metabolised very slowly by CYPs. Therefore, the potential of BGS649 drug-drug interactions is low.
Clarification of worsening of lower limb oedema to exclude measurement artefacts and effects of restrictive clothing.	To prevent inappropriate drug interruption for artefactual worsening of leg oedema.

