The doses of BGS649 [REDACTED] and dosing schedule [REDACTED] selected for use in Study MBGS205 were chosen based on results obtained in a previous study in obese male subjects with HH, which suggested that these doses were well tolerated and may normalise testosterone levels (Study CBGS649A2204). To assure 12 months each dose arm study drug exposure, subjects will continue with the same active study drug assignment from Study MBGS205 to the Study MBGS206. To keep the study blinded and offer subjects receiving placebo the benefit of active arm treatment, the placebo subjects in Study MBGS205 will be randomised to one of the active treatment arms. If one or more dosing arms are dropped during the conduct of Study MBGS205, these will not be progressed in Study MBGS206.

Aromatase inhibitors decrease oestrogen synthesis and increase pituitary luteinising hormone (LH) and follicle stimulating hormone (FSH) with a consequent stimulation of testosterone

production (de Boer et al 2005; Loves et al 2008). This increase in testosterone has multiple clinical effects, including: effect on insulin resistance, on body composition, strength and sexual and overall well-being. Therefore, additional safety, efficacy, and pharmacokinetic (PK) will be collected in subjects who completed the full 24 week treatment period in Study MBGS205. It is conceivable that up to 12 month exposure may be needed to demonstrate full treatment benefit in regards to positive effect on cardiometabolic parameters (Haider et al 2010). In addition, the improvement in body composition may be also shown consistently only after 12 months treatment (Emmelot-Vonk et al 2008).

Testosterone increase may lead to worsening certain parameters e.g. prostate-specific antigen (PSA), haematocrit. To ensure adequate safety monitoring, these parameters together with testosterone level will be monitored in the same way as in MBGS205 study (see Section 9.1.1 for a detailed description)

BGS649 has been shown to be present in semen. PK assessment of seminal fluid and plasma will be performed to determine the plasma/semen relationship to enable modelling of BGS649 semen concentration by dose in order to determine the potential transference of BGS649 to sexual partners.

This study will be conducted in compliance with the protocol and with the International Conference on Harmonisation (ICH) guidelines on Good Clinical Practice (GCP).

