10.7 Prohibited Therapy

The following classes of medication listed below are not permitted to be taken during the conduct of the study starting from Baseline. Over the counter or ordered via the internet or prescribed medications that are known to influence production or efficacy of sex hormones, or with oestrogen/androgen-like or antioestrogen/antiandrogen-like properties e.g.

- Opiates/Opioids including methadone for > 7 consecutive days during study duration
- Chronic systemic steroid treatment or systemic steroids for > 5 consecutive days for intercurrent illness (inhaled and topical steroids are allowed)
- Medications known to increase prolactin levels, e.g., antipsychotics
- 5- α -reductase inhibitors, e.g., Finasteride
- Spironolactone
- Cimetidine

- Growth hormone
- Testosterone, known testosterone enhancers, anabolic steroids, known active Fertility drugs and Oestrogens or selective oestrogen receptor modulators (SERMS)
- Clomid
- Bisphosphonates, Teriparatide, Denosumab (treatment with calcium and vitamin D for bone health is allowed at the discretion of the investigator)

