11.2.3 Cardiometabolic Parameters

Blood pressure (SBP and DBP) will be measured as part of the vital signs analysis (Section 12.8).

All blood samples are to be collected after 8 hours fasting, after ECG and vital sign measurements

HbA1c, fasting lipids (total cholesterol, LDL, HDL, triglycerides), fasting glucose and insulin and hs-CRP will be measured. In addition, HOMA-IR will be calculated to estimate insulin resistance using the following formula:

$HOMA-IR = [\text{glucose (nmol/L)} * \text{insulin } (\mu\text{U/mL})/22.5]$, where glucose and insulin must be fasting (Matthews et al 1985).

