13.4.2.4 Exploratory Endpoints

1. In subjects that were randomised to active treatment in Study MBGS205:
 - Change in exploratory parameters from Baseline in Study MBGS205 to Week 48 in Study MBGS206 by dose group
 - Body composition (weight, BMI, waist and hip circumference, and parameters measured by bio-impedance)
 - Markers of cardiometabolic disease (blood pressure, lipid profile, HbA1c, glucose and insulin, hs-CRP, and HOMA-IR)
 - Physical activity, sleeping pattern, and strength (measured by wrist worn monitors and grip strength measurement)
 - Total and domain scores on PRO measures (Sexual function (IIEF, PROMIS SexSF), Energy/fatigue (BFI, PROMIS Fatigue), SF-36)
 - The relationship between changes in PROs and changes in body composition, physical activity, grip strength, and sleep
 - The relationship between changes in testosterone and changes in cardiometabolic parameters, body composition, physical activity, grip strength, sleep, and PROs.
2. In subjects that were randomised to placebo in Study MBGS205:
 - Change in exploratory parameters from Baseline in Study MBGS206 to Week 48 in Study MBGS206 by dose group
 - Body composition (weight, BMI, waist and hip circumference, and parameters measured by bio-impedance)
 - Markers of cardiometabolic disease (blood pressure, lipid profile, HbA1c, glucose and insulin, hs-CRP, and HOMA-IR)
 - Physical activity, sleeping pattern, and strength (measured by wrist worn monitors and grip strength measurement)
 - Total and domain scores on PRO measures (Sexual function (IIEF, PROMIS SexSF), Energy/fatigue (BFI, PROMIS Fatigue), SF-36)

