##### 8.6.4.2 Changes in Cardiometabolic Disease Markers

Descriptive summary tables will be presented for blood pressure (systolic and diastolic blood pressure), fasting lipid profile (total cholesterol, low density lipoprotein [LDL], triglycerides and HDL), HbA1c, fasting glucose, fasting insulin, high sensitivity C reactive protein (hs CRP) and HOMA-IR values and change from baseline values by treatment regimen and visit.

The change from baseline in each parameter up to Week 48 will be analysed via t-test and MMRM in the same manner as the change from baseline in total testosterone (see Section 8.6.3.3). Analyses will be conducted separately for subjects that were randomised to active treatment and subjects that were randomised to placebo treatment in study MBGS205.

Non-fasting values of all lipid profile parameters, glucose and insulin will be excluded from both the descriptive summary and analysis.

In addition the number and proportion of subjects who met the definition of metabolic syndrome will be summarised by treatment regimen at each visit (baseline and post-baseline).

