### 8.8.3 Association Testing

To determine any correlation between endpoints after 12 months active treatment, various association testing will be conducted using the ITT Population in subjects that were randomised to active treatment in Study MBGS205 at Week 48. For the below sets of endpoints separate linear regression models in which changes in PRO measure total or subscale scores will be taken as the predictor variable, associated PRO baseline score as a covariate and the endpoint to be tested against as the regressor variable. Pearson's Correlation coefficients, coefficients of determination ( $R^2$  statistic) Beta coefficients, standard errors, and 95% CIs will be presented. In addition scatter graphs will be generated annotated with the coefficient of determination ( $R^2$  statistic):

- Change in PRO measures vs Change in Body Composition Parameters
- Change in PRO measures vs Change in Bio Impedance Parameters
- Change in PRO measures vs Change in Physical Activity Parameters
- Change in PRO measures vs Change in Grip Strength
- Change in PRO measures vs Change in Sleep Parameters
- Change in PRO measures vs Change in Oestradiol
- Change in PRO measures vs Change in Testosterone/oestradiol Ratio

Similar association testing will be conducted on the below endpoints using total testosterone as the predictor variable:

- Change in Total Testosterone vs Change in Cardiometabolic parameters
- Change in Total Testosterone vs Change in Body Composition parameters
- Change in Total Testosterone vs Change in Bio Impedance Parameters
- Change in Total Testosterone vs Change in Physical Activity Parameters
- Change in Total Testosterone vs Change in Grip Strength
- Change in Total Testosterone vs Change in Sleep Parameters
- Change in Total Testosterone vs Change in PRO measures

Association testing will also be conducted on the below

- Change in systolic blood pressure vs Total Testosterone, Oestradiol and Testosterone/Oestradiol ratio at Week 48
- Change in diastolic blood pressure vs Total Testosterone, Oestradiol and Testosterone/Oestradiol ratio at Week 48
- Change in Creatinine vs Blood Pressure (Absolute systolic and diastolic blood pressure) at Week 48
- Change in Creatinine vs Change in Blood Pressure (Systolic and Diastolic blood pressure) at Week 48

---

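### Insulin users may enter, but fasting insulin and HOMA-IR are analysed without regard to insulin use, so a change in insulin therapy can appear as a change in these two exploratory markers

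*Protocol*

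**What the plan says.** **Who may enter.** The Protocol's Summary and Justification of Changes removes insulin from the prohibited medications: "To enable recruitment of representative target population of obese men with type 2 diabetes requiring insulin". The current text agrees. Protocol 10.7 opens with "The following classes of medication listed below are not permitted to be taken during the conduct of the study starting from Baseline", and insulin is not in the list that follows.

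**How the marker is defined.** Protocol 11.2.3 states: "In addition, HOMA-IR will be calculated to estimate insulin resistance using the following formula". The formula is glucose times insulin over 22.5. Its only condition is "where glucose and insulin must be fasting".

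**How it is analysed.** SAP 8.6.4.2 applies a within-arm t-test and an MMRM to the change to Week 48 in fasting insulin and HOMA-IR. SAP 8.6.4 uses the ITT population. The only data rule is "Non-fasting values of all lipid profile parameters, glucose and insulin will be excluded from both the descriptive summary and analysis". The MMRM in SAP 8.6.1 contains treatment, visit, baseline and their interactions with visit, and no term for insulin use. SAP 8.8.3 adds "Change in Total Testosterone vs Change in Cardiometabolic parameters" and does not separate insulin users. The list of changes in SAP 9 does not mention insulin.

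**What is available.** SAP 7.1.4.3 classifies medications by start and stop dates relative to active drug, and SAP 8.4.4 codes and tabulates them. Neither is linked to these two markers.

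**The concern.** An eight-hour fast controls for food. It does not control for injected insulin, which may be read by the assay, may lower glucose, and may alter the man's own secretion. The product of glucose and insulin is then no longer a clean estimate of his insulin resistance. The SAP already drops samples that make a marker invalid (non-fasting ones), but this reasoning was not extended when the eligible population changed.

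The protocol names this outcome as one of interest: "This increase in testosterone has multiple clinical effects, including: effect on insulin resistance". If values from insulin users are mixed in, the within-arm test, the dose comparison and the testosterone association for these two markers are harder to interpret. A false change could arise in either direction. For men on active drug throughout, SAP 8.1.5 places baseline at the start of MBGS205, so about 48 weeks are available in which insulin therapy can change.

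**Working it through.** **1. Number of men per arm.** The documents give no SD, effect size or power for HOMA-IR. The only relevant stated figure is in the synopsis: 30 entered per dose, about 17% dropout, about 25 completers. Check: 30 × (1 − 0.17) = 24.9. This reproduces. The SAP's ITT set also requires a post-baseline lumbar scan in MBGS206, so 25 is a reasonable working n.

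**2. Is insulin use handled anywhere?** Four places could do so: the HOMA-IR definition (fasting only), the data exclusion (non-fasting only), the model terms (none for insulin), and the sensitivity or subgroup analyses for these markers (none by insulin use). None does.

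**3. Effect of one man on an arm mean.** All glucose and insulin values here are assumptions. HOMA-IR = glucose (mmol/L) × insulin (uU/mL) / 22.5, and the shift in the arm mean is the man's change divided by 25. The starting value is 8 × 20 / 22.5 = 7.11.

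| Measured insulin | Glucose | HOMA-IR at Week 48 | Change | 1 man in 25 | 3 men in 25 |
|---|---|---|---|---|---|
| 20 to 60 | stays 8 | 8 × 60 / 22.5 = 21.33 | +14.22 | +0.57 | +1.71 |
| 20 to 60 | 8 to 6 | 6 × 60 / 22.5 = 16.00 | +8.89 | +0.36 | +1.07 |
| 20 to 40 | stays 8 | 8 × 40 / 22.5 = 14.22 | +7.11 | +0.28 | +0.85 |
| 20 to 40 | 8 to 6 | 6 × 40 / 22.5 = 10.67 | +3.56 | +0.14 | +0.43 |
| stays 20 | 8 to 6 | 6 × 20 / 22.5 = 5.33 | −1.78 | −0.07 | −0.21 |

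The last row is the case in which the assay reads none of the injected insulin and his own insulin is unchanged. Even the sign depends on facts the documents do not give.

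**4. Effect of extra variance alone.** This was simulated for the within-arm t-test (n = 25, two-sided 5%, 40,000 runs per setting). The assumed true change is −1.0 in every man, and the assumed SD of change is 1.5 in non-users. With no users, power is about 89%.

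| Users in 25 | Users' SD 4 | Users' SD 8 | Users' SD 12 | Users left out |
|---|---|---|---|---|
| 2 | 75% | 54% | 40% | about 86% |
| 5 | 60% | 30% | 18% | about 81% |

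Under these assumptions, leaving users out loses less power than keeping them in.

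**5. Units.** The working takes glucose in mmol/L, the SI unit that SAP 7.1.3.11 uses for its glucose threshold. Protocol 11.2.3 prints nmol/L in the formula, which should be corrected separately.

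**The case against.** The gap itself is not in dispute; its weight is.

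- **Low stakes.** These are two items in a list of exploratory markers. Protocol 13.5.1 and SAP 8.6.1.1 treat all analyses as exploratory without multiplicity adjustment. No primary or secondary endpoint uses either marker. Protocol 7.2.1 calls it only conceivable that up to 12 months are needed to show cardiometabolic benefit; the main reason given for 12 months is bone. This stands.
- **Unknown number of users.** Every man comes from MBGS205, and these documents do not show how many were on insulin. If none were, there is no effect. This stands.
- **Stable users are partly handled.** Change from baseline and the baseline covariate remove part of a constant offset. This stands, but it leaves the extra variance and any change in insulin therapy.
- **The illustration can be made to look large.** Holding glucose at 8 mmol/L while measured insulin triples gives the highest figure in the table. Letting glucose fall to 6 cuts it by more than a third. Both are shown for that reason.
- **Exclusion can bias.** Dropping every value taken on insulin would remove the Week 48 value of a man who started insulin because his glycaemia worsened, which could flatter the drug. This stands, and it rules out that remedy as the main analysis.

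A reader might infer that injected insulin is simply counted as insulin resistance and can swamp the drug effect. The documents do not support that: the insulin assay is not described, and neither a drug effect nor an SD for HOMA-IR is given to compare with.

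**Conclusion.** The point holds as a gap in the SAP. Insulin users are an intended part of the population, and nothing in the plan separates them when fasting insulin and HOMA-IR are analysed. If any are enrolled, some values in the t-test, MMRM and association models may not measure what the marker is meant to measure, and a change in insulin therapy can appear as a change in the marker.

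The size is not computable from the documents. Among the assumed cases, one man in 25 moves the arm mean by between −0.07 and +0.57. The power figures rest wholly on an assumed change of −1.0 and assumed SDs. The consequence is limited to two exploratory markers and their association with testosterone; the bone mineral density conclusion is untouched. The change should be made because it is cheap, not because the trial depends on it.

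**What to change.** In SAP 8.6.4.2 and 8.8.3:

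1. Analyse fasting insulin and HOMA-IR in men not using insulin at their analysis baseline as defined in SAP 8.1.5, identified from the concomitant-medication records.
2. Report per arm the number of insulin users and the number who start, stop or change insulin. The documents do not say whether dose changes are recorded; if they are not, report starts and stops and say so.
3. Add a sensitivity analysis that sets values after a post-baseline insulin start to missing in the MMRM. For men who came from placebo, Week 48 is the only scheduled post-baseline sample, so this removes the man from the model.
4. Keep the all-men analysis as a supporting table.
5. Keep all men in the HbA1c, glucose, lipid and bone analyses.

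One detail needs a rule. SAP 7.2.2.3 assumes that a medication with an unclear start date began after the first MBGS206 dose, which could class a baseline insulin user as a new starter. Insulin records need their own convention.

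The cost is a few sentences, one medication flag and a slightly smaller n for two parameters. No new data or visits are needed. The sensitivity analysis conditions on a post-baseline event that may be linked to worsening glycaemia, so it should be read beside the all-men result.

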4 STUDY SYNOPSIS

Name of Sponsor/Company: Mereo BioPharma 2 Ltd	Individual Study Table Referring to Part of the Dossier:	(For National Authority Use Only)
Name of Product: BGS649		
Name of Active Ingredient: 4,4'-[fluoro-(1-H-1,2,4-triazol-1-yl)methylene]bisbenzotrile		
	Volume:	
	Page:	
Title of Study: A 6 month double-blind safety extension study of MBGS205 evaluating the effects of long term treatment with BGS649 on bone mineral density.		
Principal Investigator: [name]		
Study Centre(s): Approximately 50 sites		
Publication(s): None		
Planned Study Period: Oct 2016 to Oct 2017	Development Phase: Phase II	
Objectives:		
Primary Objective The primary objective is to evaluate the effect of 12 months treatment with BGS649 on bone mineral density (6 months treatment during Study MBGS205).		
Secondary Objectives		
Safety:		

 To evaluate the effect of BGS649 after 12 months period of treatment with active study drug (6 months treatment during Study MBGS205 and 6 months treatment during Study MBGS206) by dose group on: 
 Bone turnover biomarkers Bone mineral density and bone biomarkers by vitamin D status (Baseline vitamin D from Study MBGS205) Oestradiol levels Testosterone outside upper limit of normal range Prostate specific antigen and haematocrit Blood pressure Adverse events (AEs) To evaluate if there are associations between changes in bone mineral density after 12 months treatment with BGS649 with end of treatment testosterone and oestradiol levels To collect safety data in subjects switching from placebo arm in Study MBGS205 and treated with 6 months active study drug in Study MBGS206. 		
Pharmacokinetic		
The pharmacokinetic (PK) objective is to determine BGS649 concentration by dose in seminal fluid and relationship to plasma PK at the end of treatment		
Efficacy		

 To follow the change of total testosterone, bioavailable testosterone, luteinising hormone (LH), and follicle stimulating hormone (FSH) over a total of 12 months administration of BGS649 in those on active treatment in Study MBGS205 and a total of 6 months administration of BGS649 on subjects that were switched from placebo treatment during Study MBGS205 Evaluation of percentage of subjects with normalised testosterone after 12 months treatment with BGS649 in those on active treatment in Study MBGS205 and total of 6 months administration of BGS649 on 		

Name of Sponsor/Company: Mereo BioPharma 2 Ltd	Individual Study Table Referring to Part of the Dossier:	(For National Authority Use Only)
Name of Product: BGS649		
Name of Active Ingredient: 4,4'-[fluoro-(1-H-1,2,4-triazol-1-yl)methylene]bisbenzotrile	Volume: Page:	
subjects that were on placebo treatment during Study MBGS205		
Exploratory Efficacy Objectives		

 1. To evaluate the effect of 12 months treatment with BGS649 (6 months treatment in Study MBGS205 and 6 months treatment in Study MBGS206) on: 
 ○ Cardiometabolic parameters, body composition, physical activity, grip strength, and sleep pattern; and on sexual functioning, fatigue, and quality of life, assessed by patient reported outcomes (PROs) ○ The association between changes in PROs and changes in body composition, physical activity, grip strength, and sleep ○ The association between changes in testosterone and changes in cardiometabolic parameters, body composition, physical activity, grip strength, sleep, and PROs 2. To evaluate the 6 month efficacy data on subjects on placebo arm in Study MBGS205 treated with active study drug in Study MBGS206 (cardiometabolic parameters, body composition, physical activity, grip strength, sleep, and PROs). 		
Methodology:		

This is a 6 months, active treatment, extension study, open to subjects who have completed full 24 weeks in Study MBGS205 (A Phase IIb multicentre, double-blind, dose-ranging, randomised, placebo-controlled study evaluating safety and efficacy of BGS649 in male obese subjects with hypogonadotropic hypogonadism [HH]).
 
The main purpose of the study is to evaluate bone mineral density and other long term safety and efficacy parameters in subjects after 12 months exposure with BGS649, to better define the risk/benefit of BGS649 in the obese male HH patient. The study will also collect additional BGS649 safety and efficacy data on subjects that were randomised to placebo in Study MBGS205 and have 6 months active drug exposure in Study MBGS206.
 
Informed Consent will be taken prior to study procedures being performed. Study participation will comprise of an Extension Study Baseline visit (Week 24 of Study MBGS205), 7 visits during the treatment period up to Week 48 (End of Treatment [EOT]), and a Follow-Up (FU) visit for safety performed at Week 60, 12 weeks after the Week 48/EOT visit. The End of Study is defined as the last visit of the last global subject.
 
During the 24 week treatment period, subjects will take required dose weekly (\pm 1 day from the time schedule of regular planned dose) with water.
 
Safety assessments will include bone mineral density (by dual energy X-ray absorptiometry [DEXA] scan), vital signs, physical examination, electrocardiograms (ECGs), haematology, blood chemistry and urinalysis, bone turnover markers, prostate-specific antigen (PSA), oestradiol, and recording of AEs, serious AEs (SAEs), AEs of special interest (AESIs), and concomitant medications.
 
The safety of the study will also be periodically monitored through a data monitoring committee (DMC) and will include relevant subject data from Study MBGS205 and Study MBGS206.
 
To ensure adequate safety monitoring, serum total testosterone levels will be evaluated at each visit by an independent unblinded physician, and if subject meets discontinuation criteria (total testosterone \geq 1500 ng/dL [52 nmol/L] at any 2 consecutive time points throughout both studies MBGS205 and MBGS206), the subject will be discontinued from the treatment.
 
Efficacy assessments will include measurement of total and calculated bioavailable testosterone, LH, FSH, body composition measurement including body mass index (BMI), waist and hip circumference and impedance, cardiometabolic parameters, physical activity and sleep pattern via the wearing of wrist monitors, and grip strength via a dynamometer, and sexual functioning and satisfaction, fatigue, and quality of life via PROs.
 
Pharmacokinetics of BGS649 in plasma and seminal fluid will also be evaluated at 12 months of study drug exposure. Seminal fluid PK will be assessed (excluding subjects that are vasectomised or have vasectomy planned during the study period) at the Baseline visit (Week 24 of Study MBGS205) and Week 48 (EOT Visit 7). Subjects that are discontinued early from the study drug will provide samples for seminal fluid PK at EOT Visit 7, unless they are not able to provide this sample. Concomitantly with semen PK, plasma PK will be assessed to estimate plasma to semen BGS649 transference.
		

Name of Sponsor/Company: Mereo BioPharma 2 Ltd	Individual Study Table Referring to Part of the Dossier:	(For National Authority Use Only)
Name of Product: BGS649		
Name of Active Ingredient: 4,4'-[fluoro-(1-H-1,2,4-triazol-1-yl)methylene]bisbenzotrile	Volume: Page:	
Treatment allocation Subjects receiving active doses of BGS649 in Study MBGS205 will continue with the same dose in Study MBGS206. Subjects receiving placebo in Study MBGS205 will be randomised, using interactive response technology (IRT), on a 1:1:1 basis to each of the following active treatment arms: 
 • BGS649 [REDACTED] • BGS649 [REDACTED] • BGS649 [REDACTED] If one or more dosing arms are dropped during the conduct of Study MBGS205 these will not be progressed in Study MBGS206 and subjects switching from placebo will be randomly allocated to available dose arms.		
Number of Subjects: Enrolment will continue until 30 subjects from each of the previous active treatment arms in Study MBGS205 have entered this study aiming for approximately 25 subjects completing each dose level with 48 weeks total exposure. Assuming about 17% dropout rate in the extension study. Subjects previously treated with placebo will be enrolled until target subject population is met in all active arms.		
Diagnosis and Main Criteria for Inclusion: Inclusion 
 1. Participating in Study MBGS205 and completion of the 24 week treatment period without meeting any discontinuation criteria of Study MBGS205 2. Agreement on the part of the subjects to use double-barrier contraception for vaginal sexual intercourse with female partners of child bearing potential to prevent conception and foetal BGS649 exposure from seminal fluid. To use single barrier protection (condom) to prevent semen exposure through non-vaginal sexual intercourse with female partners of child bearing potential and refrain from sperm donation for the duration of the study. All to be continued for at least 3 months following study drug discontinuation 3. Ability to understand and comply with the requirements of the protocol/study, including understanding and being able to give informed consent 4. In opinion of the investigator has been compliant with the requirements of the Study MBGS205 protocol. Exclusion 
 1. Development of clinically significant medical or psychiatric condition during Study MBGS205 that may interfere with the study assessments or mask/mimic symptoms of hypogonadism, would prevent the subject complying with the requirements of the protocol, or would make it unsafe for the subject to participate in the study as per investigator judgment 2. Development of hypothalamic or pituitary tumour (or inflammatory condition) or suspicion of pituitary or hypothalamic tumour based on a clinical or laboratory evidence, e.g., elevated prolactin or other pituitary hormone abnormality, symptoms/signs of tumour mass effect (unless there is documentation of a normal magnetic resonance imaging scan of pituitary and hypothalamus within 3 months before Baseline) 3. Meeting any of the discontinuation criteria of initial Study MBGS205 4. Evidence of new significant prostatic disease in Study MBGS205 5. Aspartate aminotransferase (AST) or alanine aminotransferase (ALT) > 3 times the upper limit of normal (ULN) or bilirubin ≥ 2 times the ULN (unless caused by Gilbert syndrome) 6. Fragility fracture or bone mineral density T-score < -2.0 7. Use of cardiac pacemaker or other medical electronic devices that can be affected by bio-impedance assessment 8. Planned treatment with prohibited medications (including self-prescribed) 9. 12-lead ECG abnormalities at Baseline including QT_C by Fridericia's correction method (QT_CF) interval > 450 ms 10. Intention to take part in study of other investigational product during the next 36 weeks. 		

Name of Sponsor/Company: Mereo BioPharma 2 Ltd	Individual Study Table Referring to Part of the Dossier:	(For National Authority Use Only)
Name of Product: BGS649		
Name of Active Ingredient: 4,4'-[fluoro-(1-H-1,2,4-triazol-1-yl)methylene]bisbenzotrile	Volume: Page:	
Test Product, Dose and Mode of Administration: BGS649 is prepared [REDACTED] [REDACTED] Subjects will receive [REDACTED] [REDACTED]		
Reference Therapy, Dose and Duration of Administration: None.		
Duration of Treatment in Study MBG206: Subjects will be treated for maximum of 24 weeks with BGS649, with a 12 week follow-up period after completion		
Study endpoints Primary 1. Percentage change in lumbar bone mineral density measured by DEXA (g/cm ²) from Baseline in Study MBGS205 to Week 48 in Study MBGS206 by dose group in subjects randomised to active treatment in Study MBGS205. Secondary Safety 1. In subjects that were randomised to active treatment in Study MBGS205 by dose group: 
 ○ Percentage change in hip bone mineral density measured by DEXA (g/cm²) from Baseline in Study MBGS205 to Week 48 in Study MBGS206 ○ Percentage change in bone turnover markers (C-terminal telopeptide [CTx1], osteocalcin, bone alkaline phosphatase, and procollagen type 1 N-propeptide [P1NP]) from Baseline in Study MBGS205 to Week 48 in Study MBGS206 ○ Proportion of subjects with T-scores ≤ -2.5 at Week 48 ○ Percentage change in bone density and bone biomarkers adjusted for vitamin D deficiency from Baseline in Study MBGS205 to Week 48 in Study MBGS206 ○ Change of oestradiol (absolute and percentage) from Baseline in Study MBGS205 to Week 48 ○ Proportion of subjects that overshoot testosterone (total testosterone above 1000 ng/dl [35 nmol/L], from first dose of study drug in Study MBGS205 until study completion) ○ Change in PSA from Baseline in Study MBGS205 to Week 48 in Study MBGS206 ○ Change in haematocrit from Baseline in Study MBGS205 to Week 48 in Study MBGS206 ○ Change in blood pressure (systolic and diastolic) Baseline in Study MBGS205 to Week 48 in Study MBGS206 ○ Treatment emerged AE, SAE, and AESI (from first dose of study drug in Study MBGS205 until study completion) ○ Relationship between change in bone mineral density from Baseline in Study MBGS205 to Week 48 in Study MBGS206 and absolute levels of oestradiol and total testosterone at Week 48 in MBGS206 2. In subjects that were randomised to placebo in Study MBGS205 by dose group: 
 ○ Percentage change in hip bone mineral density measured by DEXA (g/cm²) from Baseline in Study MBGS206 to Week 48 ○ Percentage change in bone turnover markers (CTx1, osteocalcin, bone alkaline phosphatase, and P1NP) from Baseline in Study MBGS206 to Week 48 ○ Change of oestradiol (absolute and percentage) from Baseline in Study MBGS206 to Week 48 ○ Proportion of subjects with T-scores ≤ -2.5 at Week 48 of Study MBGS206 		

Name of Sponsor/Company: Mereo BioPharma 2 Ltd	Individual Study Table Referring to Part of the Dossier:	(For National Authority Use Only)
Name of Product: BGS649		
Name of Active Ingredient: 4,4'-[fluoro-(1-H-1,2,4-triazol-1-yl)methylene]bisbenzotrile	Volume: Page:	

 ○ Proportion of subjects that overshoot testosterone (total testosterone above 1000 ng/dl [35 nmol/L] from first dose of study drug in Study MBGS206 until study completion) ○ Change in PSA from Baseline in Study MBGS206 to Week 48 ○ Change in haematocrit from Baseline in Study MBGS206 to Week 48 ○ Change in blood pressure (systolic and diastolic) Baseline in Study MBGS206 to Week 48 ○ Treatment emerged AE, SAE, and AESI (from first dose of study drug in Study MBGS206 until study completion). 		
Efficacy		

 1. In subjects that were randomised to active treatment in Study MBGS205 by dose group: 
 ○ Percentage of subjects that have normalisation of total testosterone at Week 48 in Study MBGS206 ○ Change in total and bioavailable testosterone from Baseline in Study MBGS205 to Week 48 in Study MBGS206 ○ Change of LH and FSH from Baseline in Study MBGS205 to Week 48 in Study MBGS206 2. In subjects that were randomised to placebo in Study MBGS205 by dose group: 
 ○ Percentage of subjects that have normalisation of total testosterone at Week 48 of Study MBGS206 ○ Change in total and bioavailable testosterone from Extension Study Baseline to Week 48 in Study MBGS206 ○ Change of LH and FSH from Extension Study Baseline to Week 48. in Study MBGS206 		
Pharmacokinetics		

 1. EOT plasma and semen concentration of BGS649 by dose group. 		
Exploratory		

 1. In subjects that were randomised to active treatment in Study MBGS205: 
 ○ Change in exploratory parameters from Baseline in Study MBGS205 to Week 48 in Study MBGS206 by dose group 
 ○ Body composition (weight, BMI, waist and hip circumference, and parameters measured by bio-impedance) ○ Markers of cardiometabolic disease (blood pressure, lipid profile, HbA1c, glucose and insulin, hs-CRP, and homeostatic assessment of insulin resistance [HOMA-IR]) ○ Physical activity, sleeping pattern, and strength (measured by wrist worn monitors and grip strength measurement) ○ Total and domain scores on PRO measures (Sexual function (IIEF, PROMIS SexSF), Energy/fatigue (BFI, PROMIS Fatigue), SF-36) ○ The relationship between changes in PROs and changes in body composition, physical activity, grip strength, and sleep ○ The relationship between changes in testosterone and changes in cardiometabolic parameters, body composition, physical activity, grip strength, sleep, and PROs. 2. In subjects that were randomised to placebo in Study MBGS205: 
 ○ Change in exploratory parameters from Baseline in Study MBGS206 to Week 48 in Study MBGS206 by dose group 
 ○ Body composition (weight, BMI, waist and hip circumference, and parameters measured by bio-impedance) ○ Markers of cardiometabolic disease (blood pressure, lipid profile, HbA1c, glucose and insulin, hs-CRP, and HOMA-IR) ○ Physical activity, sleeping pattern, and strength (measured by wrist worn monitors and grip strength measurement) ○ Total and domain scores on PRO measures (Sexual function (IIEF, PROMIS SexSF), 		

Name of Sponsor/Company: Mereo BioPharma 2 Ltd	Individual Study Table Referring to Part of the Dossier:	(For National Authority Use Only)
Name of Product: BGS649		
Name of Active Ingredient: 4,4'-[fluoro-(1-H-1,2,4-triazol-1-yl)methylene]bisbenzotrile	Volume: Page:	
Energy/fatigue (BFI, PROMIS Fatigue), SF-36		

Statistical Methods:
 
Populations to be analysed:
 
The intention to treat (ITT) population includes all subjects who:
 
 1. Are randomised, and 2. Receive at least 1 dose of study medication, and 3. Provide a Baseline efficacy value and at least 1 available evaluation of efficacy post-Baseline. 
The safety population includes all subjects who received at least 1 administration of the study medication.
 
For the summary of semen concentration of BGS649, all subjects who received at least 1 administration of the study medication and have at least 1 quantifiable concentration will be included in the PK population.
 
All safety endpoints will be analysed using the safety population. All efficacy endpoints will be analysed using the ITT population.
 
Further safety and tolerability will be analysed using the safety population.
 
Primary Statistical Hypothesis: The percentage decrease from Baseline in lumbar bone mineral density measured in g/cm² by DEXA [REDACTED]
 
H0: ≤ 3%
 
H1: > 3%
 
The null hypothesis will be rejected for a dose group and the endpoint considered met if the lower bound of the 2-sided 95% confidence interval for the percentage decrease from Baseline in lumber spine is greater than 3%.
 
Assuming a 2-sided test at [REDACTED] significant level and a standard deviation of [REDACTED] to achieve 90% power N=25 subjects in each dose group would be needed to detect a [REDACTED] decrease from Baseline in bone mineral density at 48 weeks.
		
Date of the Protocol: Amended Version 2.0, 28 Mar 2017		

